8.2.1.3. Pharmacokinetics

The PK Analysis Set will include all enrolled subjects who received 1 dose of filgotinib and had at least 1 nonmissing PK concentration datum of filgotinib or its metabolite GS-829845 reported by PK lab.

8.3. Data Handling Conventions

For summary statistics, PK concentration values below the limit of quantitation will be treated as zero at predose and 1-half of the lower limit of quantitation (LLOQ) for postdose time points.

Laboratory data that are continuous in nature but are less than the LLOQ or above the upper limit of quantitation will be imputed to the value of the lower or upper limit minus or plus 1 significant digit, respectively (eg, if the result of a continuous laboratory test is < 20, a value of 19 will be assigned; if the result of a continuous laboratory test is < 20.0, a value of 19.9 will be assigned).

Missing data can have an impact upon the interpretation of the study data. As this study is of short duration, it is anticipated that missing data will be minimal. In general, values for missing data will not be imputed. However, a missing pretreatment laboratory result would be treated as normal (ie, no toxicity grade) for the laboratory abnormality summary.

8.4. Demographic Data and Baseline Characteristics

Demographic and baseline measurements, such as height, weight and BMI, will be summarized and descriptive statistics will be provided.

Demographic summaries will include sex, race/ethnicity, enrollment, and age.

8.5. Interim Analysis

Review of available safety and PK data will be conducted by the sponsor to facilitate the decision on whether or not to conduct the adaptive cohorts.

8.6. Safety Analysis

All safety data collected on or after the date that study drug was first administered up to the date of last dose of study drug plus 30 days will be summarized by hepatic function group using Safety Analysis Set.

8.6.1. Extent of Exposure

A subject's extent of exposure to study drug data will be generated from the study drug administration page in eCRF. Exposure data will be listed.

8.6.2. Adverse Events

Clinical and laboratory AEs will be coded using the current version of MedDRA. System organ class (SOC), high-level group term, high-level term, preferred term (PT), and lower-level term will be attached to the clinical database.

Adverse event data will be listed by subject. Treatment-emergent AEs (TEAEs), serious TEAEs, and TEAEs leading to discontinuation of study will be summarized by hepatic function group, SOC, and PT using the current version of MedDRA.

8.6.3. Laboratory Evaluations

Listings of individual subject laboratory results will be provided. Laboratory results and change from predose values for selected lab tests will be summarized by hepatic function group at scheduled visits. The incidence of treatment-emergent graded laboratory abnormalities will be summarized by hepatic function group.

8.6.4. Other Safety Evaluations

Vital signs and ECG data will be summarized by hepatic function group.

8.7. Pharmacokinetic Analysis

Plasma concentrations over sampling time and PK parameters (C_{max} , T_{max} , C_{last} , T_{last} , λ_z , AUC_{last} , AUC_{inf} , $\%AUC_{exp}$, $t_{1/2}$, CL/F , and V_z/F , as appropriate) for filgotinib and GS-829845 will be listed and summarized by hepatic function group using descriptive statistics (eg, sample size, mean, SD, $\%CV$, median, first quartile, third quartile, minimum, and maximum).

An analysis of variance appropriate for a parallel design will be fitted to the natural logarithmic transformation of PK parameters (AUC_{last} , AUC_{inf} , and C_{max}) for filgotinib and GS-829845. Two-sided 90% CIs will be calculated for the GLSM ratios of PK parameters between hepatic impairment group versus the matched control (normal hepatic function) group. If the 2-sided 90% CIs of the GLSM ratio for AUC_{last} , AUC_{inf} , and C_{max} of filgotinib or GS-829845 falls within the [50%, 200%] bound, the null hypothesis that subjects with hepatic impairment exhibit PK parameter change of at least 2-fold for filgotinib or GS-829845 compared with subjects with normal liver function will be rejected.

Protein binding of filgotinib and GS-829845 at their T_{max} and another later time point will be summarized by hepatic function group using descriptive statistics. Unbound PK parameters such as CL_u/F , and V_{zu}/F will be calculated as appropriate and summarized by hepatic function group. Relationships between measures of hepatic function (ie, CPT score, serum albumin, total bilirubin, prothrombin time, and International Normalized Ratio [INR]) and primary filgotinib/GS-829845 PK parameters will be evaluated.

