Vital Signs (blood pressure, pulse, respiration rate, and temperature): Screening, Days -1, 1, 3, 6, and the FU or the ET visit (if applicable)

Height: Screening

Weight: Screening and Day -1

Clinical Laboratory Tests (hematology, blood chemistry including coagulation, and urinalysis): Screening, Days -1, 1, 6, and the FU or the ET visit (if applicable)

Urine Drug, Cotinine, and Alcohol Assessments: Screening, Day -1 and the FU or the ET visit (if applicable)

12-lead electrocardiogram (ECG): Screening, Days -1, 1 (2 hours post dose), 6, and the FU or ET visit (if applicable)

Serum Pregnancy Test (women of childbearing potential only): Screening, Days -1, 6 and the FU or the ET visit (if applicable)

Serology Test (HBV, HCV, HIV): Screening

α -fetoprotein Test: Screening

Assessment of adverse events (AE) and concomitant medications will continue throughout the study. All clinical AEs and clinically significant laboratory abnormalities will be managed according to uniform guidelines detailed in protocol [Appendix 3](#)

Protocol-Specific Stopping Rules

If ≥ 2 subjects in any cohort experience the same or similar Grade 3 or Grade 4 treatment-emergent AE or confirmed laboratory abnormality that is not attributable to obvious alternative explanation (hematuria occurring in a menstruating female, creatine kinase [CK] elevation after strenuous exercise, or triglyceride elevation that is non-fasting, etc), a review of all safety data generated in subjects dosed to date will be initiated. The decision as to whether and how to proceed with further enrollment will be determined based on the safety review.

Test Product, Dose, and Mode of Administration:

A single dose of 100 mg filgotinib (1 x 100 mg tablet), in a fasted state.

Reference Therapy, Dose, and Mode of Administration:

Not applicable

Criteria for Evaluation:

Safety: Safety will be assessed during the study through the reporting of AEs, and by clinical laboratory tests, physical examinations, vital signs, and ECGs at various time points during the study.

Efficacy: Not applicable.

Pharmacokinetics: The following plasma PK parameters of filgotinib and its metabolite (GS-829845) will be calculated, as appropriate: C_{max} , T_{max} , C_{last} , T_{last} , λ_z , AUC_{last} , AUC_{inf} , $\%AUC_{exp}$, $t_{1/2}$, CL/F , and V_z/F .

Statistical Methods:**Pharmacokinetics:**

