Plasma PK parameters for filgotinib and GS-829845 will be listed and summarized by hepatic function group (normal or CPT Class A, B, or C) using descriptive statistics (eg, sample size, arithmetic mean, geometric mean, % coefficient of variation [CV], standard deviation [SD], median, minimum, and maximum).

An analysis of variance appropriate for a parallel design will be fit to the natural logarithm-transformed PK parameters (AUC_{last} , AUC_{inf} , and C_{max}) for filgotinib and GS-829845. The 90% confidence intervals (CIs) will be constructed for the geometric least-squares mean (GLSM) ratio of PK parameters for filgotinib and GS-829845 in groups of subjects with hepatic impairment versus matched controls.

Protein binding of filgotinib and GS-829845 at their T_{max} and another later time point will be summarized by hepatic function group using descriptive statistics.

Safety:

Safety data will be listed by subject and summarized by hepatic function group (normal or CPT Class A, B, or C) and frequency of event/abnormality or descriptive statistical summaries, as appropriate.

Sample Size:

With 16 (8 per group) evaluable subjects, the estimated two-sided 90% CI of the geometric least-square mean (GLSM) ratio of test vs reference groups, with regards to PK parameters (AUC and C_{max}) would be within (50%, 200%) with over 95% probability, if the estimated GLSM ratio were 1.0. This is assuming the SDs for PK parameters between subjects within each group is no more than 0.347 (or 0.203) for the natural logarithm-transformed PK parameters for filgotinib (or GS-829845). Such assumptions are supported by PK data from a prior Gilead study of filgotinib (GS-US-417-3900) with 100 mg dose in healthy volunteers.

An overage of 2 subjects per group will be enrolled in order to accommodate subject drop-outs, so a total sample size of 20 subjects (10 per group) for each cohort will be required.

This study will be conducted in accordance with the guidelines of Good Clinical Practices (GCPs) including archiving of essential documents.

GLOSSARY OF ABBREVIATIONS AND DEFINITION OF TERMS

λ_z	terminal elimination rate constant, estimated by linear regression of the terminal elimination phase of the log concentration versus time curve of the drug
%AUC _{exp}	percentage of AUC extrapolated between AUC _{last} and AUC _{inf}
°C	degrees Celsius
°F	degrees Fahrenheit
AE	adverse event
ALT	alanine aminotransferase (previously serum glutamic pyruvic transaminase)

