1.2.3. Additional Clinical Studies of Filgotinib

As of April 2017, filgotinib has been taken by more than 348 healthy volunteers or special populations (15 subjects with renal impairment), 959 subjects with RA, 153 subjects with Crohn's disease (CD) and 2 subjects with ulcerative colitis (UC), and has been generally safe and well tolerated. A detailed description of all clinical studies can be found in the IB.

In eleven Phase 1 studies conducted in healthy subjects (Studies GPLG0634-CL-101, -102, -103, -104, -105, -106, -107, -110, GS-US-417-3900, GS-US-417-3911, and GS-US-417-3916), filgotinib administered at doses of up to 450 mg once daily for up to 10 days was safe and well tolerated.

In two Phase 2a studies in subjects with RA (Study GLPG0634-CL-201 and -202), dosing with filgotinib was well-tolerated and achieved maximal efficacy at a 200 mg daily dose (American College of Rheumatology 20% improvement [ACR20] response of 75-92% at Week 4).

In two Phase 2b studies, filgotinib at total daily doses of 50 mg, 100 mg, or 200 mg, administered in addition to background therapy with methotrexate (MTX) (GLPG0634-CL-203) or as monotherapy (GLPG0634-CL-204) was safe and effective in subjects with moderately to severely active RA who had an inadequate response to MTX alone.

Currently, Phase 3 studies are ongoing in subjects with RA, UC (Phase 2b/3), and CD, and Phase 2 Proof of Concept studies are ongoing in Uveitis, Sjogren's, Lupus, psoriatic arthritis and ankylosing spondylitis, small bowel CD and fistulizing CD.

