## 1. INTRODUCTION

This statistical analysis plan (SAP) describes the statistical analysis methods and data presentations to be used in tables, figures, and listings (TFLs) in the clinical study report (CSR) for Study GS-US-417-4048. This SAP is based on Protocol GS-US-417-4048 dated 12 January 2017 and the electronic case report form (eCRF). The SAP will be finalized before database finalization. Any changes made after the finalization of the SAP will be documented in the CSR.

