### **Protein Binding Assessment**

Protein binding of filgotinib and GS-829845 will be assessed at or near their  $T_{max}$  timepoints as well as at another later time point.

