### **2.4. Changes from Protocol-Specified Analysis**

No changes from protocol-specified analyses are planned.

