### 8.1.3. Statistical Analysis Methods

#### 8.1.3.1. General Considerations

Individual subject concentration data and individual subject PK parameters including percentage of protein binding for filgotinib and GS-829845 will be listed and summarized using descriptive statistics by hepatic function group. Summary statistics (numbers of subjects, mean, SD, coefficient of variation, median, minimum, maximum, Q1, and Q3) will be presented for both individual subject concentration data by time point and individual subject PK parameters by treatment. Moreover, the geometric mean, 95% CI, and the mean and SD of the natural log-transformed values will be presented for individual subject PK parameter data.

Individual concentration data listings and summaries will include all subjects with concentration data. The sample size for each time point will be based on the number of subjects with nonmissing concentration data at that time point. The number of subjects with concentration BLQ will be presented for each time point. For summary statistics, BLQ values will be treated as zero at predose and one-half of the LLOQ for postdose time points.

Individual PK parameter data listings and summaries will include all subjects for whom PK parameter(s) can be derived. The sample size for each PK parameter will be based on the number of subjects with nonmissing data for that PK parameter.

The following tables will be provided for each analyte by hepatic function group:

- Individual subject concentration data and summary statistics
- Individual subject PK parameters and summary statistics

The following figures will be provided for each analyte by hepatic function group:

- Individual subject concentration data versus time (on linear and semilogarithmic scales)
- Mean ( $\pm$  SD) concentration data versus time (on linear and semilogarithmic scales)
- Median (Q1, Q3) concentration data versus time (on linear and semilogarithmic scales)

Individual, mean, and median postdose concentration values that are  $\leq$  LLOQ will not be displayed in the figures and remaining points connected.

The following listings will be provided:

- PK sampling details by subject, including differences in scheduled and actual draw times, and sample age
- Individual data on determination of plasma half-life and corresponding regression correlation coefficient

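### Must the SAP add unbound clearance and volume because protocol section 8.7 mentions them?

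*Protocol*

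**What the plan says.** After the main group comparison, protocol section 8.7 turns to protein binding. It then says that unbound parameters, of which CLu/F and Vzu/F are given as examples, "will be calculated as appropriate and summarized by hepatic function group".

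The protocol synopsis does not repeat this. Under its criteria for evaluation it writes "The following plasma PK parameters of filgotinib and its metabolite (GS-829845) will be calculated, as appropriate", and the list that follows contains total-drug parameters only. Under statistical methods it promises that binding at Tmax and "another later time point will be summarized by hepatic function group using descriptive statistics", and stops there.

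The SAP keeps the binding work. Its study design section states "Protein binding of filgotinib and GS-829845 will be assessed at or near their" Tmax and again later. Section 8.1.3.1 says that individual PK parameters "including percentage of protein binding for filgotinib and GS-829845 will be listed and summarized". Section 8.1.3.2 adds a summary of percent unbound by time point and group, with a subject listing. No unbound clearance, volume or exposure appears in the PK abbreviations, Table 8-2, Table 8-3 or section 8.1.3.

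SAP section 2.4 reads "No changes from protocol-specified analyses are planned". SAP section 1 reads "This SAP is based on Protocol GS-US-417-4048 dated 12 January 2017". Section 1.2.3 of the supplied protocol, however, contains "As of April 2017, filgotinib has been taken by more than 348 healthy volunteers".

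**The concern.** An SAP is expected to carry out the analyses its protocol names or to say which it drops and why. Here one named item disappears without comment, and section 2.4 says that nothing has changed.

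The item is also relevant to a hepatic impairment study. Low albumin contributes to the Child-Pugh-Turcotte score. Impaired subjects may enter with albumin down to 2.0 g/dL, while controls must be at or above the lower limit of normal. If binding depends on albumin, which the documents do not state, clearance computed from total drug could hide a difference in unbound clearance between groups.

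Binding is measured at two times, and neither document says which unbound fraction would enter the calculation. If nobody fixes that beforehand, the choice is made after the data are seen. The completeness and interpretation of the descriptive PK results would be at stake, and possibly how they are read for dosing in patients with liver disease.

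**Working it through.** **1. The protocol items against the SAP.**

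| Protocol 8.7, after the main comparison | SAP |
|---|---|
| Binding at Tmax and later, descriptive | Kept in 8.1.3.1 and 8.1.3.2 |
| Unbound parameters, conditional and descriptive | Not listed |
| PK against measures of liver function | Kept in 8.1.3.2 as Spearman correlations and plots, with albumin among the measures |

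One item of three is absent. Table 8-3 would not have held it in any case, because that table lists formal comparisons and the protocol asks only for summaries of unbound parameters. The PK abbreviations list is weak evidence of a deliberate omission. It carries entries such as Cmin, partial AUC and intravenous volume that have no place in Table 8-2, so it looks like a standard list.

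**2. Can the missing parameters be obtained from what is planned?** With fu = percent unbound / 100,

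- CLu/F = (CL/F) / fu
- Vzu/F = (Vz/F) / fu

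CL/F and Vz/F for filgotinib are in Table 8-2, and percent unbound is listed per subject. Each parameter is one division, with no new sample, assay or model.

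**3. How many outputs are missing?** Table 8-2 gives CL/F and Vz/F for filgotinib only. With normal plus three impairment classes, 2 parameters × 1 analyte × 4 groups = 8 summaries. If only Cohort 1 runs, 2 × 1 × 2 = 4. The protocol's two parameters are examples, so this counts the named ones.

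**4. Would their absence hide something?** The documents give no human binding value, only a nonclinical figure below 70%. The following is therefore an illustration under assumptions: linear binding to albumin alone, control binding b0 of 30% to 70%, and mean albumin of 4.0 g/dL in controls and 3.0 g/dL in impaired subjects.

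- The ratio of unbound fractions, control to impaired, is 1 − b0 × (1 − 3.0/4.0).
- b0 = 0.30: 1 − 0.30 × 0.25 = 0.925.
- b0 = 0.70: 1 − 0.70 × 0.25 = 0.825.
- If total CL/F does not change, these are also the impaired-to-control ratios of CLu/F.
- If total CL/F rises in proportion to the unbound fraction, the CLu/F ratio is 1.0.

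The ratio could therefore lie anywhere from 0.825 to 1.0 depending on an assumption about CL/F, so no effect size can be claimed. In both cases the cause would show in the planned table. Percent unbound would go from 70% to 70/0.925 = 75.7%, or from 30% to 30/0.825 = 36.4%. A reader would see the shift beside the CL/F summary.

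Setting the impaired mean at 2.0 g/dL would give larger effects. But 2.0 is the screening minimum for each subject, so a mean of 2.0 would need every subject to sit exactly on it.

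**5. Does section 2.4 misstate the position?** The SAP names a protocol of 12 January 2017. A protocol that reports data to April 2017 cannot be that text. The January version is not available, so whether it contained the sentence on unbound parameters is unknown. The documents do not establish that section 2.4 was wrong when written.

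**The case for a change.** The best case for a change is that conditional wording gives discretion over the decision but does not excuse leaving it unrecorded. The SAP is where such a decision belongs, and it records none. A second point is the choice between two unbound fractions. Suppose the later fraction were 10% above the Tmax value in the impaired group only, an assumed figure. Using the later value would then multiply the CLu/F ratio by 1/1.10 = 0.909, a 9% drop that depends solely on the choice. The remedy is cheap: two table entries and a sentence.

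Some of this stands. The documents do not match, and one line either way would be tidier. Two considerations limit its weight.

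First, the SAP uses the same discretion elsewhere without harm. Section 8.7 also lists CL/F and Vz/F, as appropriate, for GS-829845, and Table 8-2 leaves them out for that analyte without comment. That is sensible: the SAP defines CL/F as dose over AUCinf, and no dose of the metabolite is given.

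Second, the missing rule for the unbound fraction is missing from the protocol too, so the SAP does not depart from it. No threshold applies to unbound clearance, and because binding is reported at both times, any dependence on the choice can be checked.

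Reporting unbound AUC and Cmax ratios with confidence intervals would go beyond the protocol and is not needed to honour it.

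**Conclusion.** No change to the plan follows. This is a small documentation gap that a PK analyst can fill sensibly, and it may result only from the SAP following an earlier protocol version. Its size is 4 to 8 descriptive summaries for one analyte.

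The primary endpoints are AUClast, AUCinf and Cmax of total drug. The 2-fold rule with 90% intervals uses those parameters, and the sample size rests on their assumed log-scale SDs of 0.347 and 0.203. None of these would differ if the unbound parameters were added. The protocol also does not expect significant exposure changes with hepatic impairment.

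The conclusion rests on two assumptions: that the binding data are collected and listed as both documents plan, and that the unbound parameters remain descriptive. If unbound exposure were to enter a dosing criterion, the rule for the unbound fraction would need to be set in advance. Nothing in either document gives it that role.

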8.8. Sample Size

With 16 (8 per group) evaluable subjects, the estimated two-sided 90% CI of the geometric least-square mean (GLSM) ratio of test vs reference groups, with regards to PK parameters (AUC and C_{max}) would be within (50%, 200%) with over 95% probability, if the estimated GLSM ratio were 1.0. This is assuming the SDs for PK parameters between subjects within each group is no more than 0.347 (or 0.203) for the natural logarithm-transformed PK parameters for filgotinib (or GS-829845). Such assumptions are supported by PK data from a prior Gilead study of filgotinib (GS-US-417-3900) with 100 mg dose in healthy volunteers. An overage of 2 subjects per group will be enrolled in order to accommodate subject drop-outs, so a total sample size of 20 subjects (10 per group) for each cohort will be required.

9. RESPONSIBILITIES

9.1. Investigator Responsibilities

9.1.1. Good Clinical Practice

The investigator will ensure that this study is conducted in accordance with the principles of the Declaration of Helsinki (as amended in Edinburgh, Tokyo, Venice, Hong Kong, and South Africa), International Conference on Harmonization (ICH) guidelines, or with the laws and regulations of the country in which the research is conducted, whichever affords the greater protection to the study subject. These standards are consistent with the EU Clinical Trials Directive 2001/20/EC and Good Clinical Practice Directive 2005/28/EC.

The investigator will ensure adherence to the basic principles of GCP, as outlined in 21 Code of Federal Regulations (CFR) 312, Subpart D, "Responsibilities of Sponsors and Investigators," 21 CFR, Part 50, "Protection of Human Subjects," and 21 CFR, Part 56, "Institutional Review Boards."

The investigator and all applicable subinvestigators will comply with 21 CFR, Part 54, "Financial Disclosure by Clinical Investigators," providing documentation of their financial interest or arrangements with Gilead, or proprietary interests in the study drug under study. This documentation must be provided prior to the investigator's (and any subinvestigator's) participation in the study. The investigator and subinvestigator agree to notify Gilead of any change in reportable interests during the study and for 1 year following completion of the study. Study completion is defined as the date when the last subject completes the protocol-defined activities.

